9.4.2. Sensitivity Analyses of Primary Endpoint Analysis

The following sensitivity analyses will be performed using the same statistical method as the primary endpoint analysis, including adjusting for baseline subject characteristics of site location (United States; other countries), number of new PEx requiring IV antibiotics in the previous year (1; 2; 3); FEV1 % predicted (< 70; \geq 70); and baseline CFTR- targeting medications use (Yes; No):

- The event rate per subject per 28 weeks of PEx will be compared between the lenabasum 20 mg BID and placebo cohorts using a Poisson regression model with effects of treatment and log (subject treatment exposure duration), based on the PP population.

- The event rate per subject per 28 weeks of PEx will be compared in the lenabasum 20 mg BID and placebo cohorts using a negative binomial model with effects of treatment and log (subject treatment exposure duration), based on the mITT population. Negative binomial regression is a generalization of Poisson regression which loosens the restrictive assumption that the variance is equal to the mean made by the Poisson model.
- The event rate per subject per 28 weeks of PEx will be compared in the lenabasum 20 mg BID and placebo cohorts using a negative binomial model with effects of treatment and log (subject treatment exposure duration), based on the PP population.

9.5. Secondary Efficacy Analyses

The secondary efficacy endpoints ([Section 4.2.2](#)) will be summarized by treatment cohort. Actual values at each visit for each secondary outcome and changes from Baseline will be analyzed. The analyses and summaries of secondary efficacy endpoints will be performed on the mITT population. All secondary analyses will be at or through Visit 8, whichever is relevant, and will be done on observed values only. Two-sided p-values will be presented.

9.5.1. Event Rate per Subject per 28 Weeks of New Pulmonary Exacerbations by Secondary Definition

Analysis of endpoints for various event rates of PEx will be performed using the same method as the primary analysis in [Section 9.4.1](#).

9.5.2. Sensitivity Analyses of First Secondary Endpoint Analyses

Sensitivity analyses will be done for the first secondary efficacy endpoint only. The lenabasum cohort 20 mg BID will be compared to the placebo cohort. The same sensitivity analyses that are applied to the primary efficacy endpoint ([Section 9.4.2](#)) will be done for the first secondary efficacy endpoint.

9.5.3. Time to New Pulmonary Exacerbations

Time to first new PEx (days) for subjects with a new PEx is calculated as:

Date physician initiates antibiotic(s) for first new PEx – first dose date of study drug + 1

Time to first PEx for subjects without a new PEx (days event free) is calculated as:

Date of last dose of study product during the 28-Week treatment period – first dose date of study drug + 1

For time to first new PEx analyses, a Cox-proportional hazards (regression) model will be used for comparing the covariate-adjusted difference in event-time distributions between the active and placebo cohorts. Covariates in the model will include site location (United States; Non-United States), number of new PEx requiring IV antibiotics in the previous year (1; 2; 3); FEV1 % predicted (< 70; ≥ 70); and baseline CFTR-targeting medications use (Yes; No). Hazard ratios will be provided.

A life-table method will be used to estimate survival probabilities in 14-day intervals between Day 1 to 182 plus a final interval of ≥ 183 days. Subjects at risk, number of PEx, number of

censored in each time interval and overall, survival probability in each time interval, Kaplan-Meier estimated first quartile, median and third quartile of time, hazard ratios (lenabasum/placebo) and associated 95% CI, and log-rank p-values will be provided.

The time to PEx will be evaluated using a Kaplan Meier method. The homogeneity of event time distribution will be tested between each and overall active treatment cohorts as compared to placebo using a log-rank or a weighted log-rank test (Fleming-Harrington) in case of non-parallel curves across groups.

[figure not shown]

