4.2.2. Secondary Efficacy Endpoints

The secondary efficacy endpoints include the following, all assessed at or through Visit 8 (treatment phase), as relevant:

- Event rate of new PEx per subject per 28 weeks using secondary definition of new PEx, comparing lenabasum 20 mg BID and placebo cohorts
- Time to first new PEx using primary definition of new PEx, comparing lenabasum 20 mg BID and placebo cohorts
- Time to first new PEx using secondary definition of new PEx, comparing lenabasum 20 mg BID and placebo cohorts
- Event rate of new PEx per subject per 28 weeks, using the primary definition of new PEx, comparing lenabasum 5 mg BID and placebo cohorts.
- Event rate of new PEx per subject per 28 weeks, using secondary definition of new PEx, comparing lenabasum 5 mg BID and placebo cohorts
- Time to first new PEx using primary definition of new PEx, comparing lenabasum 5 mg BID and placebo cohorts
- Time to first new PEx using secondary definition of new PEx, comparing lenabasum 5 mg BID and placebo cohorts
- Change in CFQ-R respiratory symptom domain score for adolescents and adults, comparing lenabasum 20 mg BID and placebo cohorts
- Change in FEV1 % predicted, comparing lenabasum 20 mg BID and placebo cohorts
- Change in CFQ-R respiratory symptom domain score for adolescents and adults, comparing lenabasum 5 mg BID and placebo cohorts
- Change in FEV1 % predicted, comparing lenabasum 5 mg BID and placebo cohorts

[figure not shown]

-
-
-

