9.3. Adjustments for Multiplicity

The overall type I error rate will be controlled for primary and secondary efficacy outcomes with a fixed sequence, independent hierarchical assessment of efficacy.

The primary efficacy endpoint will be assessed first. If this comparison yields statistically significant results at two-sided alpha level of 0.05, then the secondary outcomes will be assessed in a hierarchical order for statistical significance.

The Type I error will be controlled for secondary efficacy outcomes with hierarchical assessments of efficacy at a two-sided alpha level of 0.05. If the assessment is not significant, then the analysis of the rest of endpoints will be exploratory. The order for tests for treatment effect in secondary efficacy endpoints is listed in [Section 4.2.2](#).

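### SAP section 9.5.3 does not fix which test decides the four time-to-first-PEx steps of the hierarchy, so the 5% level is not guaranteed at those steps

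*SAP*

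**What the plan says.** Section 9.3: "The Type I error will be controlled for secondary efficacy outcomes with hierarchical assessments of efficacy at a two-sided alpha level of 0.05". The order is that of section 4.2.2, and "If the assessment is not significant, then the analysis of the rest of endpoints will be exploratory". Of the 11 secondary endpoints in 4.2.2, the 2nd, 3rd, 6th and 7th are time to first PEx: 20 mg BID against placebo by the primary and the secondary definition, then the same pair for 5 mg BID.

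Section 9.5.3 describes the analysis of these endpoints in three places:

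- Cox model: "a Cox-proportional hazards (regression) model will be used for comparing the covariate-adjusted difference in event-time distributions between the active and placebo cohorts". The covariates are listed, with prior PEx as (1; 2; 3), and hazard ratios are promised.
- A list of life-table and Kaplan-Meier outputs ends with hazard ratios, their confidence intervals, "and log-rank p-values will be provided".
- Homogeneity of the event-time distributions is to be tested "using a log-rank or a weighted log-rank test (Fleming-Harrington) in case of non-parallel curves across groups".

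The section gives no criterion for non-parallel curves and no rho or gamma for the Fleming-Harrington (FH) test. Sections 6.1, 6.2, 9.3 and 9.5 do not say which of these p-values decides a step. Section 13 adds that the number of previous PEx is treated as continuous in the primary and secondary efficacy models, which differs from the categories in 9.5.3.

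**The concern.** A fixed sequence needs exactly one deciding p-value per step, settled before the treatment codes are known. Here there are up to three. Moreover, the choice between log-rank and FH depends on the shape of the curves by group, which can be judged only after unblinding. Because that is a written data-dependent rule, the problem goes beyond missing detail.

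Two analysts following the text could pass or fail step 2 on the same data, and so decide differently whether steps 3 to 11 are confirmatory or exploratory. Section 2 says the SAP supersedes the protocol's methods and, apart from analyses the FDA requests, will not be changed by the sponsor once signed. The ambiguity would therefore be locked in.

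**Working it through.** **The plan's own figure.** Section 6.3 gives 90% power for time to first PEx, from hazard ratio 0.60, event probabilities 0.60 and 0.36, and 166 per arm at two-sided 0.05. By Schoenfeld's formula:

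- events = 166 × (0.60 + 0.36) = 159.4
- z = √159.4 × |ln 0.60| / 2 − 1.960 = 12.62 × 0.511 / 2 − 1.960 = 1.264
- power = Φ(1.264) = 89.7%

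The figure reproduces. It does not identify the deciding test, because the formula serves log-rank and Cox alike and 6.3 names neither.

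**Null simulation.** 20,000 trials with no treatment effect.

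- From the SAP: 166 per arm, event probability about 0.60 over 28 weeks, 15% dropout, two-sided 0.05.
- Assumed: exponential event and dropout times, and five binary prognostic covariates with prevalences 0.40, 0.35, 0.15, 0.45, 0.50 and log hazard ratios 0.2, 0.4, 0.7, 0.3, −0.3.
- FH(ρ,γ) weights each event by w = S^ρ(1−S)^γ, with S the pooled survival estimate. The statistic is Z = Σw(x−e) / √Σw²e(1−e), where x is the treatment indicator and e the share of those at risk on active treatment.
- Monte Carlo standard error: √(0.05 × 0.95 / 20,000) = 0.15 percentage points.

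*One test named in advance:* log-rank 5.2%, adjusted Cox 5.4%, any single FH weight 5.2% to 5.3%. These are the reference levels.

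*Cox set aside; log-rank replaced by FH when a proportional-hazards pretest is significant:*

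| Pretest threshold | FH(1,0) | FH(1,1) | FH(0,1) | Better of FH(1,0) and FH(0,1) |
|---|---|---|---|---|
| 0.05 | 5.3% | 5.6% | 5.9% | 6.2% |
| 0.10 | 5.4% | 5.8% | 6.2% | 6.9% |
| 0.20 | 5.6% | 6.0% | 6.7% | 7.7% |

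*Switch when the Kaplan-Meier curves cross* (72% of null trials): FH(1,0) 4.7%, FH(0,1) 7.3%, better of the two 7.5%.

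*Smallest p-value taken:*

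| Candidates | Rejections |
|---|---|
| Cox, log-rank | 7.0% |
| Cox, log-rank, FH(1,0) | 7.9% |
| Cox, log-rank, FH(1,1) | 8.7% |
| Cox, log-rank, FH(0,1) | 9.3% |
| Cox, log-rank, all three FH weights | 10.4% |

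A second null simulation (166 per arm, 60% events, 10,000 trials) gave somewhat lower figures: log-rank alone 4.8%, pretest switch to one fixed weight 5.0% to 6.0%, switch to the better of two weights 5.8% to 7.1%, smallest p-value 7.1% to 8.0%.

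Both simulations use 166 per arm, so they describe steps 2 and 3. Steps 6 and 7 compare about 83 with about 166 subjects and were not simulated.

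**Where the error can occur.** Let step k be the first true null in the sequence. A false claim requires rejection at step k, so family-wise error is at most the level of the test used there. If k is the primary endpoint or another step that is not time to first PEx, that step's own test sets the bound. Only if k is step 2, 3, 6 or 7 do the figures above apply.

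**The case against.** The best defence is that Cox is the deciding test. It comes first in 9.5.3, it is what the section says is used for the comparison, and its covariates match the primary model. The log-rank p-value appears in a list of life-table and Kaplan-Meier outputs. The FH sentence also covers all active cohorts together against placebo, a comparison that is not in the hierarchy, which suggests supportive work. This reading is plausible but the SAP never states it. Section 9.5.3 names a p-value for the log-rank and only hazard ratios for Cox. It labels nothing supportive, whereas 9.4.1 and 9.4.2 separate the primary model from its sensitivity analyses. Section 9.5.2 limits sensitivity analyses to the first secondary endpoint.

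A second objection concerns size, and it stands. The SAP nowhere says to take the smallest p-value or to choose weights by result, and a switch to one weighted test is a natural reading. With a pretest and one fixed weight the inflation is small, and with a crossing-curve switch to FH(1,0) there is none. A reader might infer that the 5% rate is certainly broken and the control claimed in 9.3 is false. The text does not support that, because the error rate depends on a selection rule it leaves open.

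A reader might also infer that a lenient step 2 undermines every later claim. It does not: each later step must still pass its own test at 0.05.

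**Conclusion.** The gap is real and limited to secondary steps 2, 3, 6 and 7. The 5% level is not guaranteed at these steps; that is weaker than saying it is exceeded. Depending on the unstated rule, the null rejection rate is:

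- about 5% to 6.7% with a proportional-hazards pretest and one fixed weight, or up to about 7.3% with a curve-crossing switch
- about 6% to 8% with the better of two weights
- about 7% to 10% if the smallest p-value is taken

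The ambiguity itself is plain from the text. The magnitudes are less certain, since they rest on the assumed event-time, dropout and covariate distributions. The loss arises only when the earlier steps have passed and a time-to-first-PEx null is the first true null. The primary endpoint and the level of each later step's own test are untouched. The sponsor should correct this, but it does not threaten the main conclusion.

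**What to change.** Before unblinding, amend 9.5.3 as follows:

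1. Name one deciding test for secondary endpoints 2, 3, 6 and 7, for example the two-sided treatment p-value from the covariate-adjusted Cox model already specified. For error control the log-rank would serve equally well; Cox is convenient because its model and covariates are already written.
2. State whether prior PEx enters that model as categories (9.5.3) or as a continuous variable (13). Otherwise naming Cox still leaves two possible p-values.
3. Delete the switch for non-parallel curves.
4. Report the log-rank test, and any FH test with rho and gamma fixed in advance, as supportive only.

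The cost is a few sentences of SAP wording and no new data. The downside is some loss of power if the treatment effect is delayed, where a late-weighted test would do better.

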9.5.4. Continuous Variable Secondary Endpoints

Continuous variable secondary efficacy endpoints other than PEx event rate per subject per 28 week endpoints, (change from baseline in CFQ-R respiratory symptom domain score for adolescents and adults, and change in FEV1 % predicted, change in CRISS score) will be analyzed using a parametric mixed model repeated measures (MMRM). The MMRM model will include treatment, site location (United States; other countries), number of new PEx requiring IV antibiotics in the previous year (1; 2; 3); FEV1 % predicted (< 70; \geq 70); Baseline CFTR-targeting medications use (Yes; No), visit, and treatment-by-visit interaction as fixed effects, and baseline of response variable as a covariate. The parametric MMRM will use unstructured covariance matrix. Least squares means, least squares mean differences and associated 95% CI, and 2-sided p-values will be provided.

If the data are not normally distributed, then nonparametric MMRM analyses will be performed using a ranking strategy that relaxes the assumption of normality. The ranks will be assigned by a visit such that the same rank will be assigned across all treatment cohorts and placebo for a dependent variable measurement. The rank transformed nonparametric model will be analyzed including the fixed and random effects similar to the parametric MMRM model. The nonparametric MMRM model will use unstructured covariance matrix. Least squares means, least squares mean differences and associated 95% CI, and 2-sided p-values will be provided.

Two-sample t-test will be used to compare means for change from Baseline within the same group. Wilcoxon rank sum test analyses will be used to compare medians for change from baseline within the same group, in case of shift from the central tendency. Two-sided p-values will be provided.

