4.1.9. Randomization, Stratification Factors, Treatment Cohorts, and Dosing

Before dosing on Visit 1 (Day 1), eligible subjects will be randomly assigned using an Interactive Web-based Response Technology system to one of three treatment cohorts, based on a randomization schedule prepared by an independent biostatistician who was not involved in the day-to-day conduct of the study. The randomization will be stratified by number of previous new PEx requiring IV antibiotics in the previous year (“1 vs 2 or 3”; however, this changed approximately midway of study to “1 or 2 vs 3”, See [Section 13](#)), FEV1 % predicted at baseline (< 70; ≥ 70) and location of site (United States; Non-United States).

Subjects will be randomized in a 2:1:2 ratio to 1 of 3 treatment cohorts:

- Cohort 1: Lenabasum 20 mg BID, n = 166

- Cohort 2: Lenabasum 5 mg BID, n = 83
- Cohort 3: Placebo BID, n = 166

Twice per day dosing consists two doses each day with at least 8 hours between doses. Subjects will self-administer study product, which will be taken by the oral route and with no requirement as to fed or fasting state. Phase 1 data showed little impact of the fed-state on exposure to lenabasum, and subjects in all Phase 2 studies to date have taken lenabasum without regard to fed state.

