- Baseline value for comparisons to Visit 1 will be defined as the last non-missing value on or before Visit 1 and before the first dose of study product.
- Change from Baseline will be calculated as the value at post-dose minus the value at pre-dose (Baseline). Differences between treatment cohorts will be calculated as lenabasum minus placebo.
- Listings will be presented for all randomized subjects unless otherwise specified.
- All analyses will be conducted using SAS Version 9.4 or higher.
- The modified intent-to-treat (mITT) population will be the primary population for the efficacy analyses. In addition, supportive analyses using the per protocol population will be conducted for the primary efficacy endpoints and selected secondary endpoints, if relevant.
- All statistical tests will be two-sided with a significance level of 0.05 ($\alpha = 0.05$), unless otherwise specified. All p-values will be rounded to four decimal places; p-values less than 0.0001 will be presented as “<0.0001”; p-values greater than 0.9999 will be presented as “>0.9999.”

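### SAP 9.5.4 assigns independent-sample tests to within-group change from baseline, which is paired; the resulting supportive p-values would not have their nominal level

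*SAP*

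**What the plan says.** Section 9.5.4 covers the CFQ-R respiratory symptom score, FEV1 % predicted and CRISS. It first sets out a repeated-measures mixed model (MMRM), with a rank-based version if the data are not normal. Both give least squares means, their differences and 95% CIs. It then adds two further tests:

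- parametric: "Two-sample t-test will be used to compare means for change from Baseline within the same group"
- nonparametric: "Wilcoxon rank sum test analyses will be used to compare medians for change from baseline within the same group", for use if the central tendency is shifted.

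The paragraph ends: "Two-sided p-values will be provided".

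Section 6.1 defines the variable: "Change from Baseline will be calculated as the value at post-dose minus the value at pre-dose (Baseline"). It also sets the level for every test: "All statistical tests will be two-sided with a significance level of 0.05". No paired t-test, one-sample t-test or signed-rank test is named anywhere in the SAP text available.

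**The concern.** A change from baseline within one cohort is a one-sample question about differences taken within subjects. The two-sample t-test and the rank sum test assume two independent samples. If baseline values form one sample and follow-up values the other, the tests ignore the correlation between two measurements on the same subject, and the p-values do not have the stated 0.05 level.

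The practical risk is in how the report reads. A real change within a cohort, including a decline on placebo, could carry a non-significant within-group p-value while the MMRM least squares mean for the same cohort has a 95% CI that excludes zero. The point estimates need not conflict, because an unpaired test on complete pairs leaves the mean change as it is. The standard error and the p-value would differ.

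**Working it through.** **Inputs from the SAP.** Two-sided alpha is 0.05 (6.1). Cohort sizes are given in 4.1.9: "Cohort 1: Lenabasum 20 mg BID, n = 166"; "Cohort 2: Lenabasum 5 mg BID, n = 83"; placebo is also 166. With the roughly 15% dropout of 6.3, 166 becomes 166 x 0.85 = 141.

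**Not in the SAP.** The SAP gives no correlation rho between baseline and follow-up, no standard deviation, and no power for these tests. There is therefore no stated figure to reproduce. Rho is an assumption, shown as a range, and equal variance sigma² at the two time points is also assumed.

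**Standard error.** The true variance of the mean change is 2·sigma²·(1 - rho)/n. The two-sample formula uses 2·sigma²/n. The ratio of standard errors is 1/sqrt(1 - rho), whatever n is.

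**Attained alpha.** In large samples the unpaired statistic equals the paired statistic times sqrt(1 - rho), so it has standard deviation sqrt(1 - rho), not 1. It exceeds 1.960 only when the paired statistic exceeds 1.960/sqrt(1 - rho). Hence alpha = 2·[1 - Phi(1.960/sqrt(1 - rho))]. At rho 0.5, 1.960/0.7071 = 2.772 and alpha = 0.0056.

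**Power.** A paired test with 80% power has a standardised shift of 1.960 + 0.842 = 2.802. The unpaired test then has power Phi(2.802 - 1.960/sqrt(1 - rho)). At rho 0.6, 1.960/0.6325 = 3.099 and Phi(-0.297) = 0.38.

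| Assumed rho | SE ratio | Attained alpha | Power (paired test 80%) |
|---|---|---|---|
| 0.5 | 1.41 | 0.0056 | 51% |
| 0.6 | 1.58 | 0.0019 | 38% |
| 0.7 | 1.83 | 0.0003 | 22% |
| 0.8 | 2.24 | 0.00001 | 6% |
| 0.9 | 3.16 | < 0.00001 | < 0.1% |

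**Check by simulation.** Bivariate normal data with no true change were simulated, with 20,000 runs for the t-tests and 4,000 for the rank tests. At n = 166 the two-sample t-test rejected in 0.6% of runs at rho 0.5, 0.06% at 0.7 and none at 0.9. The rank sum test rejected in 0.75%, 0.075% and none. Over n = 83, 141 and 166 and rho from 0 to 0.9, the paired t-test rejected in 4.9% to 5.3% of runs and the signed-rank test in 4.4% to 5.4%. A power simulation at n = 141 gave 52%, 39%, 22%, 6% and 0.1% for the five rows of the table.

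**Direction.** At rho 0 the unpaired test holds 0.050. A negative rho would make it liberal (0.074 at rho -0.2). Repeated FEV1 or CFQ-R scores in the same subject would be expected to correlate positively, which gives the conservative direction.

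**The case against.** The strongest reply is that the SAP never says baseline values will be set against follow-up values as two samples. It says the tests are applied to change from baseline. A two-sample test on change scores needs two cohorts, and between cohorts it would be valid. On that reading the slip is the reference to a single group, the test names are right, and none of the figures above applies. The SAP does not rule this out, so the repair has to allow for it. It does not rescue the sentence, which then describes the wrong comparison and does not say which cohorts are compared. On a third reading, change scores from one cohort alone, there is no second sample and the test cannot be run. That both the parametric and the nonparametric sentence pair an independent-sample test with a single group makes an isolated typing slip less likely.

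The second reply is that nothing decisive depends on these tests, and this stands. Section 6.2 frames the secondary hypotheses as active dose against placebo. Section 9.3 controls type I error over the between-cohort comparisons listed in 4.2.2, and no within-group test is among them. Section 9.5.4 gives the CFQ-R and FEV1 comparisons to the MMRM, whose least squares means and CIs already show the change in each cohort.

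A reader might still infer that the efficacy conclusions for these endpoints are unsafe, or that false positive findings would follow. The SAP supports neither inference: the tests are outside the hierarchy, and under positive correlation they reject too seldom.

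**Conclusion.** Section 9.5.4 is wrong as written. It pairs independent-sample tests with a within-group comparison, and no other section available corrects it. If baseline and follow-up are compared as two samples, and rho lies between 0.5 and 0.9 with equal variances, the standard error is overstated 1.41 to 3.16 times, and power falls from 80% to somewhere between 51% and under 0.1%. Those sizes depend on an assumed rho and on that reading; they vanish if a between-cohort test was intended.

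The consequence is limited to supportive within-arm p-values for the CFQ-R respiratory score, FEV1 % predicted and CRISS. The correction should be made because it costs almost nothing and the p-values will be reported, not because the treatment comparison is at risk.

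**What to change.** State which comparison is intended, then name the test that matches it.

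- **Within-group change:** use the paired t-test (a one-sample t-test on the change scores) and the Wilcoxon signed-rank test. Alternatively, drop these tests and report the within-arm least squares mean change with its 95% CI from the planned MMRM.
- **Between-group change:** keep the two-sample t-test and the rank sum test, delete the words that confine them to one group, name the cohorts compared, and label the tests as supportive to the MMRM.

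The cost is an edit to two sentences and minor reprogramming; no additional data are needed. The edit is best made before signature, since Section 2 bars later sponsor changes to the SAP other than FDA-requested analyses. If the plan is already signed, the corrected analysis can be described in the clinical study report as a change from the SAP, as Section 14 provides.
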